4.3.10 DMD serum biomarker

A listing will present details regarding sample collection for evaluation of any possible DMD serum biomarker. Summary and analysis of results of the DMD serum biomarker assessment will not be included as part of this SAP but in a separate dedicated SAP.

4.4 Statistical Analysis

4.4.1 Hypothesis to be Tested

The null hypothesis being tested for the primary endpoint is that there is no difference in mean change in 4SC from baseline to 18 months between the givinostat and placebo treatment groups:

$$H_0: 4SC_{givinostat} = 4SC_{placebo}$$

The alternative hypothesis is that there is a difference in either direction in the mean change in 4SC from baseline to 18 months between the givinostat and placebo treatment groups:

$$H_0: 4SC_{givinostat} \neq 4SC_{placebo}$$

All tests will be two directional and thus references to 1-sided p-values throughout this SAP refer to significance in either direction. For all analyses, 2-sided p-values will be presented and will be subject to the relevant significance level in either direction, as stated in Section 4.4.5. Similarly, 2-sided CIs will be presented.

4.4.2 Modelling Methods

All efficacy analyses will be conducted in the target population. Formal analysis will be conducted as described in this Section for the following in the target population: the primary efficacy endpoint at 18 months, all key secondary efficacy endpoints at 18 months. All other analyses (i.e. for different endpoints or timepoints in the target population, sensitivity or supplementary analyses, or any efficacy analyses later added for the overall population) will be supportive only and will not be subject to alpha control. Therefore, nominal p-values will be presented.

The change from baseline to 18 months after treatment with givinostat or placebo for the continuous efficacy variables described in Sections 4.1, 4.2 and 4.3 will be analysed using an analysis of covariance (ANCOVA). Note that the ANCOVA analysis of muscle strength will be performed on the normalised muscle strength variable (measured in N/Kg) only. In addition, the ANCOVA analysis of NSAA will be performed on the total NSAA score only, ANCOVA analysis of PODCI scores will be performed

on the standardised scores only (for each subscale and the global function scale as completed by subject and parent), and ANCOVA analysis of MRI parameters will be performed for the fat fraction results only. In each instance, the dependent variable will be the outcome being modelled and terms for the corresponding baseline value and re-derived age at first dose (in years and months) will be included as independent covariates in the model, with randomised treatment group and concomitant steroid use (according to the 4 possible strata) included as independent classification factors. Where the dependent variable is not the muscle strength test, MRS VL MFF, PODCI score or MRI parameters, additional covariates will also be included in the model for the following baseline values (where not already included): 4SC, time to rise from floor, time to run/walk 10 metres, distance walked in 6 minutes (for the analysis of percent predicted 6MWT, this will be replaced with baseline percent predicted distance walked in 6 minutes).

Least squares means and associated 2-sided CIs will be estimated for givinostat and placebo. The treatment effect, being the difference in least squares means (givinostat-placebo), will be presented along with the associated 2-sided CI and p-value.

The need for a possible log transformation of these variables will be investigated prior to unblinding by assessing the ANCOVA model residuals without a treatment term. Where data are transformed for analysis, back transformation will be applied for the presentation of results. Presentation of the tables will be amended as needed for this, for example with the addition of an explanatory footnote.

Analysis of cumulative loss of function on the NSAA over 18 months of treatment with givinostat or placebo will be performed using negative binomial regression. The dependent variable will be the subject cumulative number of failures across all post-baseline visits. Total failed items at baseline, baseline values for: 4SC, time to rise from floor, time to run/walk 10 metres, distance walked in 6 minutes and re-derived age at first dose (in years and months) will be included as independent covariates in the model, with randomised treatment group and concomitant steroid use included as independent classification factors. The estimated cumulative number of failures across 18 months and associated 2-sided CIs from the model will be presented for each treatment group. The treatment effect will be presented as the ratio of cumulative failures for givinostat relative to placebo along with the associated 2-sided CI and p-value, where a lower ratio indicates a greater reduction in cumulative number of failures across 18 months for givinostat compared with placebo.

The binary efficacy variables (proportion of subjects with $\geq 10\%$ persistent worsening in 6MWT, proportion of subjects losing ambulation during the study) will be analysed using logistic regression. In each instance baseline values for: 4SC, time to rise from floor, time to run/walk 10 metres, distance walked in 6 minutes and re-derived age at first dose (in years and months), will be included as independent covariates. Randomised treatment group and concomitant steroid use will be included as independent classification factors. The odds ratio comparing the treatment groups will be presented, together with its associated 2-sided CI and p-value.

The time to event variables (time to 10% persistent worsening in 6MWT, time to persistent loss of standing) will be analysed using Cox proportional hazards modelling, including baseline values for: 4SC, time to rise from floor, time to run/walk 10 metres, distance walked in 6 minutes and re-derived age at first dose (in years and months) as independent covariates and randomised treatment group and concomitant steroid

use as independent classification factors. The hazard ratio will be presented, together with its associated 2-sided CI and p-value.

Where adjustment of alpha is applied to any of the above analyses per the methods described in Section 4.4.5, the 2-sided CIs will be subject to the corresponding adjustment. Thus the adjusted 2-sided CIs will be as indicated in the following table:

Analysis Time Point	Endpoint	Applicable p-value (1-sided)	Applicable p-value (2-sided)	CI (2-sided)
Final analysis	4SC at 18 months in the target population	$p \leq 0.025$	$p \leq 0.05$	95%
Final analysis	Key secondary efficacy endpoints at 18 months in the target population	$p \leq 0.025/i$ (i = rank according to Hochberg procedure)	$p \leq 0.05/i$ (i = rank according to Hochberg procedure)	$100(1-0.05/i)\%$ (i = rank according to Hochberg procedure)
General	All other analysis (supportive only)	$p \leq 0.025$ (nominal p-values presented)	$p \leq 0.05$ (nominal p-values presented)	95%

For the final analysis of key secondary efficacy endpoints at 18 months in the target population, unadjusted 95% CIs will be presented in the individual analysis tables. However, the applicable adjusted CIs following the Hochberg procedure will be given in an overall summary of these endpoints per Section 4.4.5.

Further, as a reflection of the overall totality of evidence for a treatment effect on functional outcomes, the primary endpoint and the functional key secondary endpoints (as detailed in Section 4.2.1) will be subject to assessment by Hochberg. This is equivalent to considering the primary and functional key secondary endpoints as equally important facets of the disease such that an improvement in any one, or more than one, of these endpoints can be considered to reflect a clinically meaningful benefit to the patient.

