The second key secondary endpoint associated with NSAA is the cumulative loss of function on the NSAA over 18 months of treatment with givinostat or placebo. For each subject at each post-baseline visit, failure to perform each of the 17 items of the NSAA will be assessed, where 'failure' is defined as a score transition from 2 or 1 at baseline to 0 at the respective visit. The total number of failed items for the visit will be calculated (maximum of 17 failed items per visit per subject). The subject's cumulative number of failures across all visits will be the sum of the total failures at each post-baseline visit. Subject cumulative number of failures across all post-baseline visits will be the endpoint of interest for analysis. In addition, total failed items at baseline will be calculated for each subject as the number of items with a score of 0 at the baseline NSAA assessment. Where one or more scores for the 17 items are missing, the relevant rules described in Section 4.4.4 and Appendix 7.5.4 will be followed. Note that as a result of the rule to impute any scheduled visits after early withdrawal, early withdrawal subjects will be included in the analysis using both collected and imputed assessments to calculate the cumulative number of failures post-baseline. The early withdrawal visit itself will be excluded from the cumulative number of failures across all post-baseline visits since this is an additional visit for these subjects outside of the expected scheduled post-baseline visits and would result in an inflated cumulative count. Where a subject scores zero at baseline on all items of the test, they will be excluded from the summaries and analyses of cumulative loss of function.

Summary statistics for the observed responses and change from baseline for each item included in the NSAA assessment, as well as for the total NSAA score will be presented by visit and treatment group.

Summary statistics will also be presented for baseline total items failed and for subject cumulative number of failed items across all post-baseline visits by treatment group. In addition the number and percentage of subjects meeting the above criteria for failure will be presented by visit for each of the NSAA items.

4.2.1.4 Muscle Strength Evaluated by Knee Extension and Elbow Flexion as Measured by Hand-held Myometry

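### The negative binomial model for cumulative NSAA loss does not use how many non-failed items start at 1 rather than 2, so precision on this key secondary may be lost

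*SAP*

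**What the plan says.** SAP 4.2.1.3 defines the endpoint. Failure of an item "is defined as a score transition from 2 or 1 at baseline to 0 at the respective visit", and failures are summed over the scheduled post-baseline visits. The baseline counterpart, total failed items, is "calculated for each subject as the number of items with a score of 0 at the baseline NSAA assessment".

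SAP 4.4.2 specifies the model: "The dependent variable will be the subject cumulative number of failures across all post-baseline visits". Its covariates are "Total failed items at baseline, baseline values for: 4SC, time to rise from floor, time to run/walk 10 metres, distance walked in 6 minutes" and age, with treatment and steroid stratum as factors. Baseline NSAA total score is not listed.

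For the companion endpoint, "the ANCOVA analysis of NSAA will be performed on the total NSAA score only", with "terms for the corresponding baseline value and re-derived age at first dose" as covariates. The corresponding baseline there is the baseline NSAA total. SAP 4.4.3 gives the general rule that each efficacy model carries the baseline belonging to its own endpoint.

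SAP 4.4.5 names cumulative loss as one of seven key secondaries tested by Hochberg. The end of SAP 4.4.2 also places it in a functional Hochberg family with the primary endpoint. Protocol Table 6 schedules the NSAA at screening and at randomisation, so the baseline total is already collected.

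**The concern.** Total failed items identifies the items that can no longer fail. It says nothing about how close the others are to failing. Take two boys with no item at 0, one scoring 2 on every item and one scoring 1 on every item. They have the same number of failed items, yet each of the second boy's items is one step from being counted. These are extremes, chosen only to show what information is missing.

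The failed-item count also pulls two ways: a high value means fewer items at risk, but a weaker boy.

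At stake is the width of the interval for the failure ratio, and so the chance of a positive result on this key secondary. Randomisation is stratified by steroid use only, with 110 boys planned in the target population at 2:1. A chance imbalance in baseline NSAA profile is possible, and the current terms would adjust for it only in part.

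**Working it through.** The documents state no rate, dispersion, effect size or power for cumulative NSAA loss, so there is no figure to reproduce.

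**Step 1. What baseline total adds.** Let F, n1 and n2 be the numbers of items at 0, 1 and 2 at baseline, with F + n1 + n2 = 17 (17 items, SAP 4.2.1.3). Then

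Total = n1 + 2·n2 = 2(17 − F) − n1.

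For the two boys above, F = 0. With n1 = 0 the total is 34; with n1 = 17 it is 34 − 17 = 17. With F already in the model, adding the total is the same as adding n1.

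**Step 2. What a given prognostic value would be worth.** Let R² be the partial R² of baseline total given the covariates already present. As an approximation, SE ratio = √(1 − R²). Starting from an assumed 80% power at two-sided 0.05, the new power is Φ(2.802/ratio − 1.960).

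| Assumed R² | SE ratio | Power |
|---|---|---|
| 0 | 1.000 | 80.0% |
| 0.02 | 0.990 | 80.8% |
| 0.05 | 0.975 | 82.0% |
| 0.10 | 0.949 | 84.0% |
| 0.15 | 0.922 | 86.0% |

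Example for 0.10: √0.90 = 0.949; 2.802/0.949 − 1.960 = 0.993; Φ = 0.840. Hochberg can apply smaller thresholds, so these are not power figures under the plan's own procedure.

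**Step 3. Illustrative simulation.** Inputs from the documents: N = 110, 2:1, 17 items, six post-baseline visits, and the SAP covariates including age and steroid stratum. Everything else is assumed. Noise is in simulation units, with 150 trials per row.

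| Noise in the four functional baselines | Noise in NSAA items | Median SE ratio (with/without total) | SD of estimates across trials, without → with |
|---|---|---|---|
| 0.3 | 0.4 | 0.975 | 0.099 → 0.096 |
| 0.3 | 0.8 | 0.982 | 0.080 → 0.079 |
| 0.6 | 0.4 | 0.876 | 0.122 → 0.112 |
| 0.6 | 0.8 | 0.916 | 0.096 → 0.094 |
| 1.0 | 0.4 | 0.803 | 0.131 → 0.117 |
| 1.0 | 0.8 | 0.851 | 0.135 → 0.112 |
| 2.0 | 0.4 | 0.737 | 0.164 → 0.119 |
| 2.0 | 0.8 | 0.797 | 0.143 → 0.115 |

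Spread in progression was then varied over 0.5, 1.0 and 1.5 (item noise 0.8, 120 trials each). The ratios were 0.987, 0.995 and 0.998 at functional noise 0.3, and 0.851, 0.926 and 0.960 at functional noise 1.0.

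The full range is 0.998 to 0.737, a fall in SE of 0.2% to 26.3%.

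**Step 4. Caution on the model SEs.** The last column does not rely on the fitted SE, and in some settings it shows less gain. At 0.6/0.8 it gives 0.094/0.096 = 0.979 against 0.916. At 1.0/0.4 it gives 0.117/0.131 = 0.893 against 0.803.

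Two further simulations of the same design, also with age and steroid terms, agree on direction:
- One cut the empirical variance of the log ratio by 0–21%, typically about 10%. Null rejection was about 5–8% without the total and 8–10% with it (simulation error about 1.5 points).
- The other gave SE ratios of about 0.77–0.95, with null rejection of 3–5%.

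**The case against.** The model does what the SAP says it should. The outcome counts items that leave 1 or 2 for 0, so the number already at 0 is its natural corresponding baseline, and that term is present. The four functional baselines overlap with the NSAA, whose items run from standing to a 10-metre run and include rising from the floor. The two boys in the example would be expected to differ on those timed tests, so the fitted model need not treat them alike. The model already has about ten coefficients for roughly 110 boys, and declining one more that is algebraically tied to a term already present is defensible.

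All of this stands as a defence of validity. A reader might infer that the endpoint's own baseline has been left out, that the two NSAA models follow different rules, that the failure ratio is biased, or that precision is certainly given away. The documents support none of these. SAP 4.4.3 is met, both NSAA models follow it, treatment is randomised, and nothing in the documents says how prognostic NSAA total is once the other terms are in.

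The defence does not show that the remaining information is worthless. Given F, the total still adds n1. Two of the four stand-ins are narrowed by entry criteria (Protocol 7.1: mean 4SC at most 8 seconds; rise time at least 3 and below 10 seconds). Including age and steroid stratum in the simulations did not remove the gain.

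**Conclusion.** This is an optional improvement in efficiency, of low priority; it is not an error in the plan. It is certain that the model omits the split of non-failed items between 1 and 2, and that baseline total would supply exactly that. That precision is lost is plausible but not shown.

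Under the assumed inputs:
- the SE falls by about 0–2% when the functional baselines track severity closely;
- it falls by about 4–15% with moderately noisy functional baselines (noise 1.0, item noise 0.8), depending on the spread in progression;
- it falls by 20–26% only when those baselines measure severity very poorly.

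These figures rest wholly on assumed item behaviour, noise and progression. The model-based ones may flatter the gain somewhat.

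**What to change.** In SAP 4.4.2, before unblinding, add baseline NSAA total score as a covariate in the negative binomial model for cumulative loss of function, and keep total failed items. The number of items scored 1 at baseline is an equivalent choice and may be easier to explain.

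SAP 6.0 is final, and its addendum records changes made after database lock. If the model is already locked, leave the planned model as the formal test and report the extended one as a labelled supplementary analysis with a nominal p-value.

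The cost is one degree of freedom and some collinearity with total failed items. No new data are needed.

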4.4.5 Adjustment for Multiple Comparisons

The p-value applicable to the final analysis of 4SC at 18 months in the target population will be $p \leq 0.025$ 1-sided. For final analysis of the key secondary efficacy endpoints at 18 months in the target population, adjustment for multiple comparisons will be applied as described below. For all other analyses (i.e. for different endpoints or timepoints in the target population, or analyses in the overall population), analysis will be considered supportive only. Therefore, nominal p-values will be presented and the significance level applicable will be $p \leq 0.025$ 1-sided.

In accordance with EMA (European Medicines Agency, 2002) and FDA guidelines (U.S. Food and Drug Administration, 2017), the assessment of multiple key secondary efficacy endpoints at 18 months in the target population at the final analysis will be accounted for using the Hochberg procedure (Hochberg, 1988).

The key secondary efficacy endpoints are given in [Section 4.2](#) (time to rise from the floor, 6MWT, muscle strength evaluated by knee extension, muscle strength evaluated by elbow flexion, physical function as measured by total NSAA score, physical function as measured by cumulative loss of function on the NSAA, VL MFF as assessed by MRS). Each of these endpoints will be analysed and the resulting 1-sided p-values will be ordered in descending order, from least to most significant. The highest p-value will then be compared with 0.025, the specified level of significance for the primary endpoint at the final analysis for this study, and if it is >0.025 , the subsequent p-value will be considered in relation to $0.025/2=0.0125$. As

soon as the i th endpoint has a corresponding p-value $< 0.025/i$, the treatment effects for that endpoint and all of the endpoints following it are considered to be significant. A table will be presented summarising the p-values and associated adjusted 2-sided CIs from each of the key secondary efficacy endpoints with significance indicated according to the above approach.

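### Rank-based confidence intervals for the key secondary endpoints can include no effect for an endpoint that the same table flags as significant

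*SAP*

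**What the plan says.** SAP 4.4.5 applies the Hochberg procedure to seven key secondary endpoints at 18 months in the target population: time to rise from floor, 6MWT, knee extension, elbow flexion, NSAA total score, NSAA cumulative loss of function and VL MFF.

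- Ordering: "the resulting 1-sided p-values will be ordered in descending order, from least to most significant". Rank 1 is the largest p-value and rank 7 the smallest.
- First step: "The highest p-value will then be compared with 0.025, the specified level of significance for the primary endpoint at the final analysis".
- Second step, if the first fails: "0.025/2=0.0125".
- Once a rank passes: "the treatment effects for that endpoint and all of the endpoints following it are considered to be significant".

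The table in SAP 4.4.2 gives these endpoints a 2-sided threshold of 0.05/i and an interval of 100(1-0.05/i)%, and defines i as the rank in the Hochberg procedure. The individual analysis tables keep unadjusted 95% intervals, but "the applicable adjusted CIs following the Hochberg procedure will be given in an overall summary of these endpoints per Section 4.4.5". Under SAP 4.4.5, that summary shows p-values, adjusted intervals and the significance result together. SAP 4.4.1 makes the reporting 2-sided: "For all analyses, 2-sided p-values will be presented and will be subject to the relevant significance level in either direction".

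**The concern.** The flag and the interval use different thresholds for the same endpoint. The step-up rule carries significance to every endpoint after the first passing rank, whatever its own 0.05/rank threshold. The interval still applies that threshold, and it is strictest for the endpoints with the smallest p-values. A reader of the summary table could meet an endpoint marked significant whose interval covers no effect (a difference of 0, or a ratio of 1 for NSAA cumulative loss) and could not tell which to believe. In addition, the confidence level depends on the observed rank, so the intervals, though labelled adjusted, have no guaranteed joint coverage. What is at stake is the reporting and reading of the formal key secondary results, not the decisions themselves.

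**Working it through.** **Inputs.** Seven endpoints, a starting level of 0.025 1-sided (0.05 2-sided), the ordering and the step-up rule come from SAP 4.4.5. The interval level 1-0.05/i comes from SAP 4.4.2. The p-values, effects and correlations below are assumptions.

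**The plan's own figure.** The second-step threshold is 0.025/2 = 0.0125 1-sided, or 0.025 2-sided. It reproduces.

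**When flag and interval disagree.** Let i* be the first rank that passes. An endpoint at rank j ≥ i* is significant. Its interval at level 1-0.05/j excludes no effect only if p_j < 0.05/j. The two disagree when

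0.05/j ≤ p_j < 0.05/i*.

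The reverse case (interval excludes no effect, endpoint not flagged) cannot occur, because p_j < 0.05/j would itself have been a pass.

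**Example A.** Normal-theory intervals, with each estimate scaled to 1:

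| Rank | 2-sided p | 0.05/rank | Level | Interval | Flag |
|---|---|---|---|---|---|
| 1 | 0.045 | 0.0500 | 95% | 0.022 to 1.978 | significant |
| 2 | 0.040 | 0.0250 | 97.5% | -0.091 to 2.091 | significant |
| 3 | 0.035 | 0.0167 | 98.33% | -0.135 to 2.135 | significant |
| 4 | 0.030 | 0.0125 | 98.75% | -0.151 to 2.151 | significant |
| 5 | 0.020 | 0.0100 | 99% | -0.107 to 2.107 | significant |
| 6 | 0.015 | 0.0083 | 99.17% | -0.085 to 2.085 | significant |
| 7 | 0.010 | 0.0071 | 99.29% | -0.044 to 2.044 | significant |

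Rank 1 passes (0.045 < 0.05), so all seven are significant. Six of the seven intervals include 0, and only the endpoint with the largest p-value has one that does not.

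**Example B.** p = 0.30, 0.022, 0.020, 0.018, 0.015, 0.012, 0.009. Rank 1 fails and rank 2 passes (0.022 < 0.025), so ranks 2 to 7 are significant. The intervals at ranks 3 to 7 include 0.

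**Frequency.** Seven equally correlated z-statistics were simulated, 40,000 trials per setting. The table shows the share of trials with at least one such mismatch, among trials with at least one significant endpoint:

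| Correlation | mean z 1.5 | 2.0 | 2.5 | 3.0 |
|---|---|---|---|---|
| 0 | 0.8% | 2.4% | 6.0% | 6.6% |
| 0.3 | 3.0% | 5.2% | 6.9% | 6.0% |
| 0.6 | 7.8% | 9.0% | 8.3% | 6.5% |
| 0.8 | 15.7% | 14.6% | 11.8% | 8.4% |

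The reverse mismatch occurred in none of these trials.

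**Joint coverage.** If the seven effects are independent and so far apart that the ranks are effectively fixed, joint coverage is the product of (1-0.05/i) for i = 1 to 7:

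0.95 × 0.975 × 0.9833 × 0.9875 × 0.99 × 0.9917 × 0.9929 = 0.877.

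Simulation (200,000 trials per setting) gave about 82% with all mean z = 2.5 and correlation 0, about 86% to 87% with correlation 0.5, and about 95% to 96% when no endpoint has an effect. The shortfall therefore depends on the true effects.

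**Check of the remedy.** Use level 1-0.05/i* for every endpoint. Significant endpoints have p_j ≤ p_i* < 0.05/i*, so their intervals exclude no effect. Earlier ranks j < i* failed, so p_j ≥ 0.05/j > 0.05/i*, and their intervals include it. If nothing passes, every p_j ≥ 0.05/j ≥ 0.05/7, so at i = 7 every interval includes it. In Example A (i* = 1) the lower limits become 0.022 to 0.239. In Example B (i* = 2) ranks 2 to 7 have lower limits of 0.021 to 0.142, and rank 1 includes 0. Agreement was complete in all simulated trials.

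**The case against.** The strongest reply is that i may already mean the step at which the procedure passes: SAP 4.4.5 uses i for that step, and SAP 4.4.2 speaks of intervals that follow the procedure. On that reading the contradiction disappears. But 4.4.2 defines i only as rank, 4.4.5 numbers the endpoints by rank, and neither says that one value applies to all seven. If the stopping rank was meant, the text still has to say so.

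The examples place the p-values where the rule fails, and the simulated frequencies are modest. That stands: the mismatch is conditional. The 95% intervals in the individual tables also remain available. They do not settle the summary table, which shows different intervals beside the flag.

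Two obvious replacements do worse against the flag. With unadjusted 95% intervals, change the largest p in Example A from 0.045 to 0.060: no rank passes, yet six of the seven intervals exclude 0, which is the anti-conservative direction. With 99.29% for all seven, every interval in Example A includes 0 (each p exceeds 0.0071) although all seven endpoints are significant. In a separate simulation over the same range of assumptions, the share of all trials with a mismatch was 0.4% to 7.9% under the SAP rule, 24% to 81% with unadjusted 95% intervals, and 6% to 63% with 99.29% throughout. This objection is right, and it determines the remedy.

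A reader might go further and infer that the key secondary error rate is uncontrolled or that the significance calls are unreliable. The documents do not support that: significance is decided on ordered p-values alone. Nor does the SAP claim simultaneous coverage for these intervals, so the shortfall breaks no stated promise.

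**Conclusion.** The point holds as a reporting fault. As written, the summary table can flag an endpoint significant beside an interval that includes no effect, whenever 0.05/j ≤ p_j < 0.05/i*. Under the assumed equal correlations (0 to 0.8) and mean z (1.5 to 3.0), this affects 0.8% to 15.7% of trials with a significant key secondary endpoint. The error is conservative relative to the flag. Hochberg decisions, type I error, power and the primary analysis are untouched.

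Separately, the rank-based intervals do not in general give 95% joint coverage. The 87.7% figure assumes independent, well-separated effects and is not a general value.

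The argument assumes that each interval and its p-value come from the same test, so that one excludes no effect exactly when the other is below the matching level. The endpoints with the smallest p-values get the highest confidence levels. A reader might infer that they also get the widest intervals, but the endpoints are in different units and widths cannot be compared across them.

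**What to change.** 1. In the SAP 4.4.2 table, define i for the interval column as the single rank i* at which the procedure first passes, applied to all seven endpoints, with i = 7 (99.29%) if none passes.
2. Correct the two threshold columns for these endpoints. 0.05/i (0.025/i 1-sided) is the level tested at step i, not a criterion that each endpoint must meet at its own rank.
3. Add Hochberg-adjusted p-values to the summary table. For rank j this is the smallest value of i × p_i over i = 1 to j; in Example A it is 0.045 for all seven.
4. State that the intervals match the test decision but are not simultaneous 95% intervals. This matters: at i* = 1 all seven are ordinary 95% intervals, with joint coverage of 0.95^7 = 0.698 if they are independent and the level is taken as fixed.
5. Label any other 95% intervals for these endpoints as unadjusted and not for judging significance.

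The cost is SAP and table-shell wording only. No data, test or decision changes.
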